5.5 Prior and Concomitant Therapy

Permitted: Subjects are expected to be on stable dose pharmacotherapy with one of the antidepressants listed in protocol Section 4.1 (Inclusion Criteria). Any other medication change, including initiation, discontinuation, or dose adjustment of medication, needs to be discussed with the site PI and approved before implementation.

Prohibited: Initiation of medication listed in protocol Section 4.2 (Exclusion Criteria) is not permitted during either phase of the study. Dose adjustment or initiation of permitted medications (Section 4.1 Inclusion Criteria) after enrollment must be approved by the site PI prior to implementation.

5.6 Packaging and Labeling

The NeuroStar XPLOR system will be clearly labeled with the following warning:

“CAUTION – Investigational Device when used with individuals younger than 18 years of age. Limited by Federal (or United States) law to investigational use”

5.7 Blinding of Study

The blinded TMS coils will arrive from Neuronetics and will be identical in appearance and labeled generically (i.e Coil X and Coil Y). The device will recognize one coil as active and the other coil as sham. Once a participant has been randomized, the device will “link” the participant’s treatment with the corresponding coil. The device will remain inactive if the “incorrect” coil is used for a subject, adding an additional safeguard for each participant and the integrity of the study and allow the treaters to remain blinded to the nature of the subject’s treatment.

As outlined in protocol Section 5.2, subjects will be randomly assigned to a coil and will receive all treatments during Phase I of the trial using this coil. Neither the subject nor the study staff (including those administering rTMS treatments and those administering mood, cognitive, safety, and imaging assessments) will know whether the subject is receiving active or sham treatment.

In Phase II of the trial, based upon clinical response in Phase I, subjects will be assigned to either Acute Treatment (Arm 1) or Maintenance Treatment (Arm 2). All treatments during phase II will be provided with the known-active coil.

To minimize any source of bias, unblinding of the study will not be done until all subjects have completed both Phase I and Phase II treatments. However, unblinding will occur if the Data and Safety Monitoring Board deems it necessary due to critical, unexpected patient care considerations (such as in the event of a high rate of unexpected serious adverse events).

5.8 Receiving, Storage, Distribution and Return

5.8.1 Receipt of Investigational Devices

NeuroStar™ XPLOR TMS Systems will be purchased by MCR and MUSC from Neuronetics, Inc. The devices will be delivered to and installed by Neuronetics in the TMS Suites at MCR and at MUSC.

Upon receipt of the NeuroStar and study treatment supplies, an inventory will be performed and a device accountability log completed by designated study staff at each site. The designated study staff will count and verify that the shipment contains all the items noted in the shipping invoice. Any discrepancies or damaged or unusable devices in a given shipment will be documented in the device accountability log. The MUSC Principal Investigator, [name], will notify the regulatory sponsor, [name], immediately of any discrepancies or damaged or unusable products. It will be the responsibility of the regulatory sponsor to immediately notify Neuronetics of any discrepancies or damaged or unusable products at either site.

5.8.2 Storage

The NeuroStar device will be housed in the TMS Suites at MCR and MUSC.

The supplies and disposables required for each treatment, as outlined in protocol Section 5.1, will be stored in a supply station separate from clinical stock at each site.

5.8.3 Distribution of Study Device

The NeuroStar XPLOR device will be housed in the TMS suite at the respective study sites. Subjects in Phase I will be randomly assigned to one of the blinded treatment coils at time of enrollment, as outlined in protocol section 5.2. All subjects in Phase II will be treated with the known-active, non-blinded therapy coil. All subjects will receive a treatment positioning cap during the time of their initial imaging scans; they will receive new treatment disposables (protocol section 5.1) from their treatment site at the start of every new treatment. These treatment packs and SenStar shields will be stored in an area that is separate from clinical stock. Regular reconciliation of SenStar shields received from Neuronetics, SenStar shields used during study treatments, and SenStar shields remaining will be performed. This reconciliation of the inventory will be logged in the Device Accountability Log, signed, and dated. Any discrepancies noted will be documented, the site investigator and regulatory sponsor will be notified, and an investigation will be conducted to determine the cause of the discrepancy. Any SenStar shields disposed of for

any reason other than use for the study (i.e., it was found to be defective or to be missing items) will be documented in the Device Accountability Log at the time of disposal.

5.8.4 Return or Destruction of Study Device

[figure not shown]
The NeuroStar devices purchased from Neuronetics, Inc. will remain at the study sites at the completion of the study. Any SenStar shields and treatment packs that are remaining in the inventory at the completion of the study will be packaged and shipped back to Neuronetics.

6 Study Procedures

CONFIDENTIAL

6.1 Study Overview

Figure 3 – Overview of Two-Phase Study Procedures

See Appendix E for description of mood, safety, and cognitive assessments.

6.2 Phase I – Randomized, Double-Blinded

Study Overview

Adolescents will be screened and enrolled in the study and randomized to either the active treatment or sham treatment group. Neither the subjects nor the investigators will know whether the treatments are active or sham in nature. All subjects will have baseline imaging for neurolocalization of L-DLPFC, mood, safety, and cognitive assessments. Subjects at the MCR site will have baseline magnetic resonance spectroscopy (MRS) at the time of the neurolocalization scan. All subjects will then undergo 30 rTMS treatments at their respective site within the 6- to 8-week timeframe. Mood, safety, and cognitive assessments will be performed at regular intervals throughout the study (Table 4). After the final treatment (i.e. treatment #30 or at early withdrawal), the mood and cognitive assessments will be performed for all subjects. MCR subjects will have MRS scans performed at these time points as well. These assessments may also occur monthly and at 6-month follow-up for those electing to not move on to Phase II treatment opportunities. The treatment and assessment schedules for Phase I are identical for both the active and the sham treatment cohorts. For participants at the MCR site, MRS scans will also occur after the final treatment and again at the 6-month follow-up visit.

Subjects may decline to complete any study assessment or measurement and still remain in the study so long as the assessment or measure in question does not directly impact the ability of study staff to conduct critical study procedures (ex. MRI for treatment localization, measures needed to determine eligibility, etc.) and does not impact the ability of study staff to assess the subject's continued safety (i.e., any of the Safety Assessments).

Table 4 – Phase I Schedule of Assessments (Active and Sham)

Day(s)	Pretreatment		6-Week Acute Treatment						Follow-Up	
	Screening	Baseline	Week 1 1-5	Week 2 6-10	Week 3 11-15	Week 4 16-20	Week 5 21-25	Week 6 26-30	Monthly 60, 90, 120, 150, 180	Final 210
Informed Consent	X									
KSADS	X									
Eligibility Checklist and Verification CRF	X									
Medical/Psychiatric History	X									
Urine Pregnancy Test	X									
Urine Drug Test	X									
Pre-TEEQ-P		X								
Pre-TEEQ-A		X								
Post-TEEQ-P								X ^g		
Post-TEEQ-A								X ^g		
Vital Signs ^{f,g,h,i}		X		X		X		X	X ⁱ	X
Mood Assessments										
CDRS-R ^{f,g,h}	X	X		X		X		X	X ⁱ	X
QIDS-A17-SR ^{f,g,h}	X	X		X		X		X	X ⁱ	X
CGI-S ^{f,g,h}	X	X		X		X		X	X ⁱ	X
CGI-I ^{f,g,h}				X		X		X	X ⁱ	X
Y-MRS ^{f,g,h}	X	X	X	X	X	X	X	X	X ⁱ	X
C-VAS ^c			X	X	X	X	X	X		
Cognitive Assessments										
D-KEFS ^g			X					X		X
CAVLT-S ^g			X					X		X
Safety Assessments										
C-SSRS ^{d,f,g}	X	X	X	X	X	X	X	X	X	X
TASS	X									
Adverse Event Monitoring ^e			X	X	X	X	X	X	X	X
MRI Safety Screening Questionnaire			X					X ^g		X
Imaging Assessments										
MRI localization of L-DLPFC		X								
¹ H-MRS (MCR site only)		X						X ^g		X
TMS Procedures										
Motor Threshold Determination		X	X	X ^f	X	X ^f	X	X		
TMS Treatment ^a (5 days/week)										

Phase I Schedule of Assessments Footnotes

- a. Subjects are randomized to either the active or sham treatment arm prior to first TMS treatment in Phase I.
b. Motor threshold determination is conducted utilizing the unblinded, known-active treatment coil (Coil C).
c. C-VAS is performed daily pre- and post-treatment.
d. C-SSRS is performed weekly during treatment.

- e. Subjects are assessed daily for adverse events during treatment.
f. Assessed at the post-10 and post-20 treatment visit.
g. Assessed at the post-30 treatment visit OR at time of withdrawal for TMS treatment drop-outs.
h. Monthly follow-up assessments may be conducted via telephone
i. Optional monthly assessments

6.2.1 Consent and Screening Visit

The consent/assent form will be explained in detail to the subjects and their parent(s), and any questions or concerns about the study will be addressed. Written consent/assent will be obtained from both the subject and their parent(s). See Appendices H and I.

The screening process to determine subject eligibility will occur at the respective study sites and will consist of physician evaluation and review of medical record to confirm subject meets other inclusion criteria (Section 4.1) and does not have contraindications to study treatment (Section 4.2). The following assessments will be performed at this visit:

Depression Assessments (estimated 30-45 min):

- K-SADS
- CDRS-R
- QIDS-A17-SR
- CGI-S
- YMRS

Safety Assessments (estimated 20 min):

- C-SSRS
- TASS
- MRI Safety Screen
- urine drug screen
- urine pregnancy screen (for females)

6.2.2 Baseline Visit

Subjects who are found to be eligible are randomized to one of the blinded treatment coils as outlined in protocol Section 5.2. The following assessments will be performed for all subjects:

Mood Assessments (estimated 20-30 min):

- CDRS-R
- QIDS-A17-SR
- CGI-S
- YMRS

Cognitive Assessments (estimated 60 min):

- D-KEFS
- CAVLT-2

Safety Assessments (estimated 10-15 min):

- C-SSRS

Other Assessments (estimated 10 min):

- Pre-TEEQ-P
- Pre-TEEQ-A
- Vital Signs (to include height, weight, blood pressure, and heart rate)

rTMS Procedures (estimated 30-45 min):

- Motor threshold determination

Imaging Assessments

- MRI Safety Screening Questionnaire
- MRI localization of L-DLPFC (estimated 20-30 minutes)
- ¹H-MRS (estimated as an additional 20 minutes - MCR site only)

6.2.3 TMS Treatment Days 1-10

rTMS Procedures:

- TMS treatment (37.5 min)

Depression Assessment (estimated 5 min):

- C-VAS (pre and post treatment)

Safety Assessments (estimated 10-15 min):

- C-SSRS (assessed weekly)

6.2.4 Post Treatment 10 Assessment (Performed after Treatment 10 but before Treatment 11)

rTMS Procedures:

- Motor threshold determination

Mood Assessments:

- CDRS-R
- QIDS-A17-SR
- CGI-S
- CGI-I

YMRS

Safety Assessments:

- C-SSRS

Other Assessments (estimated 5 min):

- Vital Signs

6.2.5 TMS Treatment Days 11-20

rTMS Procedures:

- TMS treatment

Depression Assessment:

- C-VAS (pre and post treatment)

Safety Assessment:

- C-SSRS (assessed weekly)

6.2.6 Post Treatment 20 Assessment (Performed after Treatment 20 but before Treatment 21)

rTMS Procedures:

- Motor threshold determination

Depression Assessments:

- CDRS-R
- QIDS-A17-SR
- CGI-S
- CGI-I

YMRS

Safety Assessments:

- C-SSRS

Other Assessments (estimated 5 min):

- Vital Signs

6.2.7 TMS Treatment Days 21-30

rTMS Procedures:

- TMS treatment

Depression Assessment:

- C-VAS (pre and post treatment)

Safety Assessment:

- C-SSRS (assessed weekly)

6.2.8 Post Treatment 30 or Early Withdrawal Assessment (Performed within 5 business days of Treatment 30 or notification of Early Withdrawal)

Mood Assessments:

- CDRS-R
- QIDS-A17-SR
- CGI-S
- CGI-I
- YMRS

Cognitive Assessments:

- D-KEFS
- CAVLT-2

Safety Assessments:

- C-SSRS

Other Assessments (estimated 10 min):

- Post-TEEQ-P
- Post-TEEQ-A
- Vital Signs

Imaging Assessments:

- ¹H-MRS (MCR site only)

Subjects will be offered the opportunity to enter into Phase II of the study at completion of this visit by their site's study team. Those choosing to continue to Phase II will follow the treatment schedule outlined in Section 6.3. Those electing not to participate in Phase II will continue with the schedule as outlined below.

6.2.9 Monthly Post-Study Monitoring (+/- 2 weeks)

Monthly post-treatment monitoring may be conducted in-person (preferred), by telephone, or by videophone. Subjects for whom this scheduled may cause an undue time or travel burden may be given the option to complete abbreviated, safety-only screens for post-treatment months 1-5. If a subject reports a concern during the safety screen, the PI will determine whether they should be scheduled for a follow-up visit (in-person, telephone, or video phone) or whether more immediate action is needed.

Depression Assessments (optional):

- CDRS-R
- QIDS-A17-SR
- CGI-S
- CGI-I
- YMRS

Safety Assessments:

- C-SSRS
- Adverse event monitoring

Other Assessments (estimated 5 min):

- Vital Signs
- Change in medication/therapy monitoring

6.2.10 Six-Month Final Visit (+/- 2 weeks)

Depression Assessments:

- CDRS-R
- QIDS-A17-SR
- CGI-S
- CGI-I
- YMRS

Cognitive Assessments:

- D-KEFS
- CAVLT-2

Safety Assessments:

- C-SSRS
- Adverse event monitoring

Other Assessments (estimated 5 min):

- Vital Signs
- Change in medication/therapy monitoring

Imaging Assessments:

- ^1H -MRS (MCR site only)

6.3 Phase II – Non-Randomized, Open-Active

Study Overview

Subjects from Phase I will be offered the opportunity to continue with rTMS treatments in Phase II and assigned to treatment arms according to their clinical outcomes at the completion of Phase I. Adolescents from both the active and sham cohorts who do not meet clinical criteria for response (CDRS-R score ≥ 28 and/or CGI-I score ≥ 3) will be given active treatment (protocol Section 6.3.1). Subjects from both the active and sham cohorts who do meet response criteria (CDRS-R score of < 28 and CGI-I score of 1 or 2) will be given maintenance treatment (protocol Section 6.3.2).

6.3.1 Phase II Acute Treatment (Arm 1) – Nonresponder Cohort

Phase I Completion assessments (protocol Section 6.2.8) will be used for Phase II Baseline assessments. A urine drug and pregnancy test will be performed before beginning active treatment for Phase II. Schedule of treatments and assessments will follow that of Phase I (protocol Sections 6.2.3 – 6.2.10) using the known-active coil. See Table 5.

Table 5 – Phase II Acute Treatment (Arm 1)
Schedule of Assessments

Day(s)	Screening	6-Week Acute Treatment						Follow-Up	
		Week 1 1-5	Week 2 6-10	Week 3 11-15	Week 4 16-20	Week 5 21-25	Week 6 26-30	Monthly 60, 90, 120, 150, 180	Final 210
Urine Drug Test	X								
Urine Pregnancy Test	X			X			X	X ⁱ	X
Vital Signs ^{a,f,g,i}					X				
Mood Assessments									
CDRS-R ^{a,f,g, h}			X		X		X	X ⁱ	X
QIDS-A17-SR ^{a,f,g, h}			X		X		X	X ⁱ	X
CGI-S ^{a,f,g, h}			X		X		X	X ⁱ	X
CGI-I ^{a,f,g, h}			X		X		X	X ⁱ	X
Y-MRS ^{a,f,g, h}			X		X		X	X ⁱ	X
C-VAS ^c		X	X	X	X	X	X		
Cognitive Assessments									
D-KEFS ^{a,g}							X		X
CAVLT-S ^{a,g}							X		X
Safety Assessments									
C-SSRS ^{a,d, h}		X	X ^f	X	X ^f	X	X ^g	X	X
TASS									
Adverse Event Monitoring ^e		X	X	X	X	X	X	X	X
MRI Safety Screening Questionnaire							X ^g		X
Imaging Assessments									
¹ H-MRS (MCR site only)							X ^g		X
TMS Procedures									
Motor Threshold Determination ^b			X ^f		X ^f				
TMS Treatment ^b (5 days/week)		X	X	X	X	X	X		

Phase II Acute Treatment Schedule of Assessments Footnotes

- a. Post-30 Assessments from Phase I are used for Phase II Baseline.
- b. Motor threshold determination and all treatments in Phase II are conducted utilizing the unblinded, known-active treatment coil (Coil C).
- c. C-VAS is performed daily pre- and post-treatment.
- d. C-SSRS is performed weekly during treatment.
- e. Subjects are assessed daily for adverse events during treatment.
- f. Assessed at the post-10 and post-20 treatment visit.
- g. Assessed at the post-30 treatment visit OR at time of withdrawal for TMS treatment drop-outs.
- h. Monthly follow-up assessments may be conducted via telephone
- i. Vital signs include height, weight, blood pressure, and heart rate
- Optional monthly assessments

6.3.2 Phase II Maintenance Treatment (Arm 2) – Responder Cohort

Phase I Completion assessments (protocol Section 6.2.8) will be used for Phase II Baseline assessments. A urine drug and pregnancy test will be performed before beginning active treatment for Phase II. Treatments will be administered using the parameters outlined for Phase I utilizing the known-active therapy coil on a biweekly basis for 52 weeks. See Table 6 for schedule of treatments and assessments.

Table 6 – Phase II Maintenance Treatment (Arm 2) Schedule of Assessments

Treatment(s)	Screening	12-Month Bi-Weekly Maintenance Treatment		Follow-Up Six Months
		1-25	26	
Urine Drug Test	X			
Urine Pregnancy Test	X			
Vital Signs ^{a,d,e,f}		X	X	X
Mood Assessments				
CDRS-R ^{a,d,e}		X	X	X
QIDS-A17-SR ^{a,d,e}		X	X	X
CGI-S ^{a,d,e}		X	X	X
CGI-I ^{a,d,e}		X	X	X
Y-MRS ^{a,d,e}		X	X	X
C-VAS		X	X	
Cognitive Assessments				
D-KEFS ^{a,e}			X	X
CAVLT-S ^{a,e}			X	X
Safety Assessments				
C-SSRS ^{a,d,e}		X	X	X
TASS				
Adverse Event Monitoring ^c		X	X	X
MRI Safety Screening Questionnaire ^a			X	X
Imaging Assessments				
¹ H-MRS (MCR site only) ^a			X	X
TMS Procedures				
Motor Threshold Determination ^{a, b}		X		
TMS Treatment ^b (5 days/week)		X	X	

Phase II Maintenance Treatment Schedule of Assessments Footnotes

- a. Post-30 Assessments from Phase I are used for Phase II Baseline.
- b. Motor threshold determination and all treatments in Phase II are conducted utilizing the unblinded, known-active treatment coil (Coil C).
- c. Assessed at every visit
- d. Assessed monthly during maintenance treatment
- e. Assessed at final (post-26) treatment OR at time of withdrawal.
- f. Vital signs include height, weight, blood pressure, and heart rate.

6.3.2.1 Every Other Week Treatment Visits (+/- 3 business days)

rTMS Procedures:

- TMS treatment (bi-weekly)
- Motor threshold determination (monthly)

Depression Assessments (assessed monthly):

- CDRS-R
- QIDS-A17-SR
- CGI-S
- CGI-I
- YMRS
- C-VAS (performed pre- and post-treatment)

Safety Assessments (assessed monthly):

- C-SSRS

Other Assessments (estimated 5 min):

- Vital Signs

6.3.2.2 Post Treatment 26 Visit (Within 5 business days of Last Treatment)

Depression Assessments:

- CDRS-R
- QIDS-A17-SR
- CGI-S
- CGI-I
- YMRS

Cognitive Assessments:

- D-KEFS
- CAVLT-2

Safety Assessments:

- C-SSRS

Other Assessments (estimated 5 min):

- Vital Signs

Imaging Assessments:

- MRI Safety Screening Questionnaire
- ¹H-MRS (MCR site only)

6.3.2.3 Six-Month Follow-Up Visit (+/- 2 weeks from 6 months post Last Treatment)

Depression Assessments:

- CDRS-R

- QIDS-A17-SR
- CGI-S
- CGI-I
- YMRS

Cognitive Assessments:

- D-KEFS
- CAVLT-2

Safety Assessments:

- C-SSRS
- Adverse event monitoring

Other Assessments (estimated 5 min):

- Vital Signs
- Change in medication/therapy monitoring

Imaging Assessments:

- ^1H -MRS (MCR site only)

7 Statistical Plan

7.1 Sample Size Determination

Preliminary data from the 2011 Wall et al. pilot study[1] was used to estimate the sample size needed per treatment group to achieve at least 80% power for detecting a difference between the active and sham treatments using 2 versions of the CDRS-R depression inventory measured at baseline and completion of 30 sessions including: 1) the rate of those responding to treatment based on a CDRS-R and CGI-I finite cutoff score (binary), and 2) the raw change in CDRS-R score from baseline (continuous).

For the binary response we observed a success rate of 71% in our preliminary study. For sample-size purposes we hypothesize a success rate of 65% for rTMS. We further hypothesize a success rate of 25% for the Sham group. Based on these assumptions, we have determined that a total sample-size of N=70 (35 per group) will provide statistical power (two-tailed, alpha=0.05) of 94% to detect a difference between groups.

When the change in CDRS-R was quantified using a continuous variable we observed a mean delta of 33.3 with corresponding standard deviation of 7.3. Under the conservative assumption that the “true” standard deviation of this response is 10.0, we have determined that a total sample-size of N=70 (35 per group) will provide statistical power (two-tailed, alpha=0.05) of 91% to detect a difference between groups of 8.0 units.

Thus a total sample-size of N=35 per group will provide adequate statistical power. Since the primary analysis will be performed using the approach of LOCF, we will not adjust the sample-size to account for attrition. We will however, perform supplementary analyses which are restricted to subjects who complete the study. Under the assumption that the attrition rate is approximately 30% we repeated the power analyses described above using an effective sample-size of N=50 (25 per group). Using these effective sample-sizes, the supplemental

analysis restricted to study completers will have statistical power of 83% to detect the hypothesized difference when change in CDRS-R is quantified as a binary response and statistical power of 80% to detect a difference between groups of 8.0 units when the change in CDRS-R is quantified as a continuous variable.

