1.3 Clinical Data to Date

The 2011 Wall et al. open-label trial (conducted under IDE number G060269) that treated a total of 7 antidepressant-resistant adolescents demonstrated a robust response rate noted by 5 of 7 subjects achieving remission of depression as rated by the Childhood Depression Rating Scale - Revised (CDRS-R). Furthermore, CDRS-R mean depression severity responses were noted to be significant by treatment #20 with correlated improvement as demonstrated with the self-report Quick Inventory of Depressive Symptoms – Adolescent Version (QIDS-A17-SR) (Figure 1). Placebo response rates in open-label trials of adolescents are a well-known phenomenon. However, the adolescents treated in our initial protocol demonstrated enduring mood improvement 6 months following their final treatment session. Furthermore, 7 of 8 subjects completed the entire treatment course – with 1 dropping out after a total of 5 minutes of treatment due to scalp discomfort and a perceived “lack of improvement”.

Figure 1 – CDRS-R and QIDS-A17-SR Response in Depressed Adolescents in an Open-label rTMS Trial (Wall, et al. J Clin Psychiatry, 2011. 72(9): p. 1263-1269

Evidence from the currently proposed study would extend these initial findings and begin to answer questions relating to the neurobiological basis of those who show response or remission of depression with rTMS treatment and those who do not respond.

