4.4 Early Withdrawal of Subjects

4.4.1 When and How to Withdraw Subjects

Subjects will be withdrawn from the study immediately if a seizure, DSM-IV-confirmed treatment-induced mania, or other UADE occurs. Subjects will also be withdrawn from the study, at the time of notification of study staff, if at any point they meet any of the exclusionary criteria outlined in protocol Section 4.2.

Subjects enrolled in Maintenance Treatment (Arm 2) in Phase II will be withdrawn from the study if they experience a worsening of their depression. Worsening of depression will be defined as a CDRS-R score increase of >33% of Phase II baseline or a raw CDRS-R score of ≥ 40 , whichever occurs first, accompanied by clinician determination of significant

clinical deterioration as noted by a clinical global improvement (CGI-I) scale score of ≥ 6 (much worse or very much worse). Worsening of suicidal ideation and behavior will be defined as an increase of the Columbia – Suicide Severity Rating Scale (C-SSRS) suicidal ideation score of ≥ 4 or suicidal behavior including actual suicide attempts, interrupted/aborted attempts, or preparatory acts or behavior. These subjects will be referred to the care of their primary clinician or psychiatric provider. Subjects and families will be given recommendations for alternative treatment options and will be offered care through the clinic. There are no funds to pay for psychiatric hospitalization of a subject in this study; however, research staff and physicians will be available at all times to evaluate subjects with adverse behavioral consequences and, if necessary, arrange for admission to a local hospital.

Subjects may decide to withdraw from the study at any time, for any reason, including inability to tolerate study treatment, lack of improvement of depressive symptoms, or worsening of depressive symptoms. There are no currently-known risks associated with abrupt discontinuation of treatment with rTMS.

Subjects will be encouraged to remain compliant with all prescribed medications and expected study visits. Nonadherence to expected study visits and/or medications will be documented and may result in removal from the study. This will be clearly discussed during the consent/assent process and reinforced throughout the study through regular screening for changes in medications or issues with compliance.

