4.4.2 Data Collection and Follow-up for Withdrawn Subjects

To enhance the validity of study data, as well as to provide subjects with ongoing monitoring and safety assessments by a qualified professional, subjects who choose to withdraw from the interventional portion of the study will be offered the opportunity to complete mood, cognitive, safety, and imaging assessments as per the study protocol.

5 Study Device

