7.3 Subject Population(s) for Analysis

The primary analysis will use the intention-to-treat (ITT) population, defined as all patients who started at least one treatment session. Secondary analyses of the primary outcome will examine “completer” and “partially adherent” cohorts. The Completer Cohort will be defined as subjects treated according to the protocol with fewer than 10 rescheduled, missed, or partially completed rTMS sessions ultimately taking part in 30 treatment sessions. The Partially Adherent Cohort will have at least 20 completed or partially completed sessions without reaching the full 30-treatment threshold. Those with less than 20 completed or partially completed rTMS sessions will be analyzed within the intention-to-treat population.

8 Safety and Adverse Events

All Unanticipated Adverse Device Effects (UADEs) and severe, expected adverse events (AEs) at least probably related to the study treatment not meeting the criteria of UADE, including mania, exacerbation of depression, and suicidality will be recorded on the Adverse Event CRF and reported according to severity and the relationship of the AE to rTMS. Records of these events will be maintained and reports submitted to the FDA, regulatory sponsor, and reviewing IRBs according to local IRB policy and regulatory requirements. All other expected clinical adverse events and nonsignificant (not serious) clinical adverse events will be reported to all Principal Investigators on a periodic basis and reported to the appropriate IRB at the time of continuing review and to the FDA at the time of the Annual Report. Expected clinical adverse events and anticipated adverse device effects are those listed in Section 1.5.2.

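### Section 7.1 sets attrition aside because LOCF is primary, but uses one set of effects for both the full sample and completers; the 94% and 91% primary powers are therefore conditional and should be stated so

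*Combined protocol and SAP*

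**What the plan says.** Section 7.1 aims for 80% power or more on two versions of the CDRS-R outcome, measured from baseline to the end of the 30 sessions: response (65% active, 25% sham) and raw change (8.0 units, SD 10). With 35 per group it states 94% and 91%.

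On dropout it says: "Since the primary analysis will be performed using the approach of LOCF, we will not adjust the sample-size to account for attrition". For a supplementary completer analysis it continues: "Under the assumption that the attrition rate is approximately 30% we repeated the power analyses described above", now with 25 per group, and states 83% and 80%. The effects are the same in both calculations; only the sample size changes.

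Other sections bear on what a dropout contributes:

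- Section 7.3 makes ITT primary, "defined as all patients who started at least one treatment session". It also provides for a partially adherent cohort with "at least 20 completed or partially completed sessions without reaching the full 30-treatment threshold".
- Section 4.4.1 lets subjects leave for reasons "including inability to tolerate study treatment, lack of improvement of depressive symptoms, or worsening of depressive symptoms".
- Section 4.4.2 says that those who withdraw from treatment "will be offered the opportunity to complete mood, cognitive, safety, and imaging assessments as per the study protocol".
- Section 1.3 reports "5 of 7 subjects achieving remission of depression" in the pilot and, separately, that "7 of 8 subjects completed the entire treatment course".

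The Study Summary plans 75 subjects (38 active, 37 sham). LOCF is named only in 7.1. Section 7.2 gives no model for continuous CDRS-R change and no dropout rule for binary response.

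**The concern.** Carrying the last score forward keeps every randomised and treated subject in the denominator. It does not give a subject who left after a few sessions the outcome of a full course. Keeping N at 35 per group therefore does not by itself preserve the power calculated for the treatment-30 effect.

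Section 7.1 does not say whether 65%/25% and 8.0 units describe everyone who starts treatment or those who finish. If they describe finishers, the primary analysis has less power than 94% and 91%, by an amount that depends on what dropouts retain. A reader cannot then tell whether the plan's own 80% target is met at the plan's own attrition figure, and a null primary result could be read as stronger evidence of no effect than it is. LOCF also ties the CDRS-R contrast to when and why subjects leave each arm.

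**Working it through.** **Inputs from the documents:** two-sided alpha 0.05; 65% vs 25%; 8.0 units, SD 10; 35 and 25 per group; attrition 30% (all 7.1); planned 38/37 (Study Summary); pilot 5 of 7 in remission and 7 of 8 completing (1.3).

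**Assumed, because the documents do not give them:** equal attrition by arm, and the share f of the effect that dropouts keep.

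**Step 1. Reproduce the stated powers.**

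Binary, pooled-variance normal approximation: power = Φ{[d − 1.96·√(2p̄(1−p̄)/n)] / √([p₁(1−p₁)+p₂(1−p₂)]/n)}, with d = 0.40 and p̄ = 0.45.

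- n = 35: (0.40 − 1.96 × 0.1189)/0.1089 = 1.53, giving 93.7% (stated 94%).
- n = 25: (0.40 − 1.96 × 0.1407)/0.1288 = 0.96, giving 83.2% (stated 83%).

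Continuous, two-sample t-test with noncentrality 8/(10·√(2/n)):

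- n = 35: 3.347 on 68 df, giving 91.0% (stated 91%).
- n = 25: 2.828 on 48 df, giving 79.1% (80.7% by normal approximation; stated 80%).

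All four reproduce with identical effects in both populations.

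**Step 2. What using the same effects implies.** With attrition a in each arm, the full-sample effect is k times the completer effect, where k = (1 − a) + a·f. The two are equal only if k = 1, that is f = 1.

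- *ITT reading.* 94% and 91% stand, and the completer figures are likely conservative. If 8.0 is the ITT difference and f = 0, completers differ by 8/0.7 = 11.4 units and 25 per group gives 98%, not 80%.
- *Completer reading.* The full-sample effect is multiplied by k.

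**Step 3. Size on the completer reading, a = 0.30.** The binary outcome is taken two ways: both arms' rates scaled (0.65k vs 0.25k), or sham held at 25% (0.25 + 0.40k vs 0.25). The continuous difference is 8k with SD 10. Example at f = 0.5, 38/37: k = 0.85; difference 6.8; standard error 10·√(1/38 + 1/37) = 2.31; noncentrality 2.94; power 82.8%.

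| f | Binary, both scaled, 38/37 | Binary, sham held, 38/37 | Continuous, 38/37 | Same three at 35/35 |
|---|---|---|---|---|
| 0 | 75.2 | 70.8 | 66.7 | 72.2 / 67.8 / 63.7 |
| 0.25 | 81.7 | 79.2 | 75.5 | 79.0 / 76.4 / 72.5 |
| 0.5 | 87.3 | 86.2 | 82.8 | 84.9 / 83.7 / 80.1 |
| 0.75 | 91.8 | 91.5 | 88.5 | 89.9 / 89.5 / 86.3 |

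**Step 4. Against the 80% target.** At 38/37 it is met once f reaches 0.18 (both scaled), 0.27 (sham held) or 0.40 (continuous). At 35 per group the thresholds are 0.29, 0.37 and 0.50.

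**Step 5. Pilot attrition.** With a = 1/8 and f = 0, k = 0.875. At 38/37, power is 88.9%, 88.1% and 84.9%.

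**Step 6. Repeated-measures alternative.** This is the power for the treatment-30 difference of 8.0 units, from the generalised least-squares variance with SD 10. Assumptions: monotone missingness at random, 70% with all three visits, dropouts' last score anywhere from none to post-20, and visit correlation 0.3–0.7 (exchangeable or first-order autoregressive). Power is 81–88% at 38/37 and 78–85% at 35 per group.

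**The case against.** The ITT reading is natural. Section 7.1 attaches the effects to all 70 subjects, and 7.3 makes ITT primary. The 65% is already below the pilot's 71%, and counting the pilot dropout as a failure gives 5/8 = 62.5%, close to it. The 8.0 units are worded as a difference to detect, and repeating a detectable difference at a smaller N is ordinary sensitivity reporting. The 30% is used only to stress a supplementary analysis. This stands as far as it goes: on that reading the primary powers are correct. But 7.1 also ties the outcomes to the end of 30 sessions, and 5/7 leaves out the dropout, so the text does not settle the matter.

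Zero retention is also an extreme. The pilot's CDRS-R response was significant by treatment 20 (1.3), a withdrawal assessment is due within 5 business days of notification (6.2.8), and some non-completers may have 20 or more sessions. This stands too, and it is why the figures are a range and not a prediction.

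Unequal attrition can move power either way. At 35 per group, with dropouts counted as nonresponders, 20% active/40% sham attrition gives 52% vs 15% and 92% power; 40%/20% gives 39% vs 20% and 41%. No document supports either pattern; the example only shows that the equal-attrition condition matters.

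A repeated-measures model exchanges one assumption for another and, at 81–88%, falls below the stated 91%. That is a fair cost.

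A reader might infer that the power figures are miscalculated, or that the trial is underpowered and needs more subjects. The documents support neither. The arithmetic is right, and the 80% target holds on the ITT reading and over much of the completer range.

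**Conclusion.** The reason given for setting attrition aside does not hold as worded. Under equal attrition, the full-sample and completer powers can both be right only if dropouts carry forward the full treatment-30 effect, and the plan neither states nor defends that. Each set alone is correct under one reading.

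The consequence is conditional. On the ITT reading there is no loss. On the completer reading, at 38/37 with an assumed 30% attrition in each arm and 0–75% of the effect kept, primary power is about 71–92% (binary) and 67–89% (continuous). It misses the 80% target only if dropouts keep less than about 18–27% (binary) or 40% (continuous). These are illustrations, not bounds. The 75 planned subjects help a little: the five above 70 are 6.7% of enrolment and are not described as an attrition allowance. The flaw in the reasoning is clear and the size of the loss is not. The text should be corrected; the sample size need not change.

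**What to change.** 1. **Section 7.1.** Drop the argument that LOCF removes the need to consider attrition. State which population 65%/25% and 8.0 units describe. Give primary ITT power at 30% attrition as a range against the 80% target, naming the share of effect kept, attrition by arm and how each arm's rate changes.
2. **Continuous CDRS-R change (7.2).** Use a mixed model for repeated measures on the scheduled post-10, post-20 and post-30 scores, with baseline CDRS-R as covariate. Map early-withdrawal scores to the nearest scheduled visit by a stated rule, and keep LOCF as a sensitivity analysis. Say plainly that the target becomes the treatment-30 difference under missing at random, and report that model's own power (about 81–88% at 38/37 under the assumptions above) separately from the LOCF range.
3. **Binary response (7.2).** State one rule for dropouts, for example nonresponders with LOCF as sensitivity, and base the conditional power on it. On the completer reading with equal 30% attrition, that example rule gives about 75% at 38/37 (both rates scaled, f = 0), and about 89% at 1-in-8 attrition.

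Cost: wording, slightly more analysis, a missing-at-random assumption, and a less favourable stated power. No patients, visits or assessments are added, because these scores are already scheduled at each point and at withdrawal.
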